2.3.1 Potential Risks

Subjects may experience short-term discomfort and bleeding of the gums from periodontal probing as a result of the periodontal clinical examinations. This exam is not different from what would normally be performed in a dental or periodontal office to evaluate the condition of the periodontal tissues and extent of disease. No dental radiographs will be taken.

Subjects may experience short-term gingival inflammation, halitosis or bad mouth taste, dental plaque accumulation, and bleeding of the gums from refraining from all oral hygiene procedures (i.e., tooth brushing, flossing or use of interdental aids and/or mouthwashes) in the two selected sextants (up to 6 teeth in each arch) for 21 days. Subjects may continue plaque control procedures for the remaining four sextants using fluoride dentifrice and toothbrush. At the completion of the study, adult prophylaxis (for orally healthy individuals) or Scaling and Root Planing (SRP) (for individuals with periodontal disease) will be completed to restore gingival health eliminating gingival bleeding, dental plaque accumulation, and halitosis. Subjects will be monitored for safety every week and after the induction of experimental biofilm overgrowth through 21 days. Any site undergoing clinical attachment loss of >2mm from the baseline measurement will be deemed as “progressing” and participant will be exited from the study and given scaling and root planing treatment as a rescue therapy at the same day of the visit.

Subjects may experience mild to moderate discomfort, and bleeding during the scaling and planing procedure or adult prophylaxis. Transient bacteremia can occur after dental prophylaxis and SRP. Standard of care practices will be utilized for all scaling and root planing, adult prophylaxis and dental exams performed. In order to minimize discomfort, subjects will receive local anesthesia prior to scaling and root planing procedures. Although not required, subjects may receive topical anesthesia prior to and during the adult prophylaxis.

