3.2 Study Outcome Measures

Primary study outcomes measured for individuals in each group (healthy and severe periodontitis):

- Expression of AIM2 and IFI16 levels will be quantified by IHC and qRT-PCR
- Periodontal clinical measurements
- Composition of oral microbiota by 16S rDNA (Illumina)

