5.1 Subject Inclusion Criteria

In order to be eligible to participate in this study, an individual must meet all of the following criteria:

- Subjects must have read, understood and signed an informed consent form.
- Subjects must be able and willing to follow study procedures and instructions.
- Subjects must be adult males or females with a minimum of 18 years (inclusive).
- Subjects must present with at least 20 teeth in the functional dentition, excluding third molars.
- Subjects must have at least 2 natural adjacent teeth in two posterior sextants that will be selected for baseline gingival biopsy and SIBO gingival biopsy.
- Subjects must be in good general health, as evidenced by medical hx (exclusion conditions defined under subject exclusion criteria below).
- Females of child-bearing capacity must be willing to have pregnancy test to confirm they are not pregnant.
- Subjects must be in the healthy (PPC-A, PPC-B) or severe periodontitis (PPC-E, PPC-G) categories according to the PPC (1).

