6.2 Visit 2: Baseline

(Day 0 +/- 5 days)

- Study personnel will update medical history, including concomitant medication, enquire about potential adverse events related to the dental exam performed during screening and ask continuance criteria questions.
- Study personnel will record the subject's vital signs (blood pressure and pulse).
- A dental examiner will verify the previously performed intraoral exam and assess for potential adverse events.
- Dental examiner will perform a comprehensive periodontal screening examination that includes Plaque Index (PI), Gingival Index (GI), Pocket Depth (PD), Bleeding on Probing (BOP) and Clinical Attachment Levels (CAL).
- The dental examiner will collect two separate subgingival plaque samples from the interdental sulcus of the teeth that are selected for a gingival biopsy (see appendix II). Dental implant sites will not be considered for subgingival plaque samples.
- A small gingival tissue biopsy sample will be removed from underneath the papillae, buccally and lingually, to include the col area of depth of the osseous crest. Biopsies will be collected by a study dentist and performed under local anesthesia. Absorbable sutures will be used to close the interproximal papillae.
- The dental examiner will deliver 1 customized acrylic stent that will be used in a different sextant from the one that the biopsy was performed. The sextant selected will be the right posterior sextant (maxillary or mandibular), except when fewer than two teeth are present and adjacent without significant diastema.
- The participant will be instructed to defer oral hygiene measures in the experimental sextant, to wear the customized stents during brushing and to discontinue flossing throughout his/her mouth. The participant will continue to use his/her standard toothpaste and toothbrush. Participants will be informed to avoid crunchy or sticky food (e.g. apples and carrots), and use of mouthwashes during baseline through visit 5 (Day 21).
- Subjects will be monitored for safety every week during the induction of experimental biofilm overgrowth through 21 days. Any site undergoing CAL

increase of >2 mm from the baseline measurement will be deemed as “progressing.” That site will not be included in data analysis, and will receive scaling and root planing treatment as a rescue therapy.

- Subjects will be given parking vouchers for the UNC Dogwood parking deck and scheduled to return for visit 3.

6.3 Visit 3

(Day 7 +/- 5 days)

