The SIBO model only induces a transient gingival inflammation without any addition of further periodontal attachment loss. The model was previously used and results support the safety of the model with no further loss of periodontal attachment (47-49). If test sites demonstrate a clinical attachment loss of more than 2 mm during the study, subjects will be removed from the study and receive rescue therapy (Scaling and Root Planing) at the same day of the visit. Clinical attachment loss will be automatically calculated by the entry software used in the study (Dental ToolKit) and compared longitudinally to the baseline clinical attachment level measurement. Previous publications from our group

demonstrated that the SIBO model is safe by having no subjects required to withdraw from previous SIBO studies due to clinical attachment loss (47-49).

Clinical Assessments and Data Collection

UNC Modified Gingival Index (GI), Loe and Silness

Full mouth gingival scores shall be visually assessed by segmenting marginal and papillary units, 6 sites per tooth: distobuccal, buccal, mesiobuccal and distolingual, lingual, mesiolingual surfaces.

0 = Normal gingiva

1 = Mild inflammation; slight change in color, slight edema. No bleeding on probing.

2 = Moderate inflammation:redness, edema, and glazing. Bleeding on probing

3= Severe inflammation; marked redness and edema. Ulceration. Tendency for spontaneous bleeding.

UNC Modified Plaque Index (Green & Vermillion)

Full mouth plaque assessment shall be assessed using the UNC Modified Plaque Index (Greene and Vermillion). Plaque scores shall be visually assessed at **6 sites per tooth** (distobuccal, buccal, mesiobuccal and distolingual, lingual, mesiolingual surfaces) on a scale of 0-3.

0 =No debris or stain present on the clinical crown.

1 =Soft debris covering not more than 1/3 of the clinical crown (cervical 3rd), or presence of extrinsic stains without other debris regardless of surface area covered.

2 =Soft debris covering more than 1/3, but not more than 2/3 (middle 3rd) of the clinical crown.

3 =Soft debris covering more than 2/3 of the clinical crown

Pocket depth (PD): Linear distance from the gingival margin (GM) to base of the pocket. If a PD reading falls between two millimeter readings, the rule shall be to round down and the lower of the two readings will be recorded.

Bleeding on Probing (BOP): Presence or absence of bleeding to manual probing recorded as a dichotomous variable.

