0- No bleeding within 10 seconds after probing.

1- Bleeding within 10 seconds after probing.

Clinical Attachment Level (CAL): Linear distance from the cemento-enamel junction (CEJ) to base of the pocket. If a CAL reading falls between two millimeter readings, the rule shall be to round down and the lower of the two readings will be recorded.

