11.3 Final Analysis Plan

1) (Primary) compare the expression (fold-change relative to baseline) of AIM2 and IFI16 between healthy (PPC-A, PPC-B) and severe periodontitis (PPC-E, PPC-G) subjects during an acute inflammatory response using the stent-induced biofilm overgrowth model

3) (Exploratory) correlate the expression of these proteins with periodontal pathogens

For the primary hypotheses involving gingival tissue samples, univariate and multivariate nonparametric testing procedures for SIBO experiments (Preisser, Sen and Offenbacher, 2011) will be utilized. In particular, a multivariate Wilcoxon Signed Rank test will use all available data to jointly test for changes in AIM2 and IFI16 expression levels over time (visit 2 to visit 5). If the overall multivariate test is statistically significant at the 0.05 level, then univariate Wilcoxon Signed Rank tests will be applied to AIM2 and IFI16 proteins individually. Similar procedures will be applied for expression levels from mRNA and from immunohistochemistry. Additionally, multivariate and univariate Wilcoxon Rank Sum Tests will be applied at the 0.05 significance level to compare SIBO-induced temporal change in Aim2 and IFI16 expression levels between healthy and severe periodontitis subjects.

Parametric statistical procedures will be used to summarize and test periodontal clinical measurements related to secondary hypotheses. Means and their 95% confidence intervals will be used to summarize measurements at each time point in healthy and severe periodontitis subjects. As these measurements will be collected at visits 2, 3, 4 and 5, linear mixed models will be used to assess change over time within groups and differences in change over time between healthy and severe periodontitis groups.

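### Sections 2.3.1, 6.2 and 7.1 give conflicting rules for a site that loses more than 2 mm of attachment, and 6.2 drops that site from the analysis, which biases CAL change toward no loss

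*Combined protocol and SAP*

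**What the plan says.** Three places in the combined protocol and SAP define what happens when attachment loss from baseline exceeds 2 mm.

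- **2.3.1 Potential Risks.** Triggered by any site. The "participant will be exited from the study and given scaling and root planing treatment as a rescue therapy", on the day of the visit.
- **6.2 Visit 2: Baseline.** Also triggered by any site, but the action is on the site: "That site will not be included in data analysis, and will receive scaling and root planing treatment as a rescue therapy". Participant exit is not mentioned, nor is same-day timing.
- **7.1 Study Procedures/Evaluations.** Triggered by test sites: "If test sites demonstrate a clinical attachment loss of more than 2 mm during the study, subjects will be removed from the study", with same-day rescue.

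Section 7.1 also reports "no subjects required to withdraw from previous SIBO studies due to clinical attachment loss".

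CAL is an outcome as well as a safety measure. Section 3.2 lists "Periodontal clinical measurements" among the outcomes, and the protocol summary names CAL as one of them. Section 11.3 says that "linear mixed models will be used to assess change over time within groups" and to compare change between groups, using visits 2 to 5. Neither 11.3 nor the withdrawal rules in 5.4 say how excluded sites, exited participants or post-rescue data are handled.

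**The concern.** There are two problems.

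**No single rule.** The entry software computes attachment loss against baseline, so a trigger will be seen and staff must act on it. Under 2.3.1 or 7.1, a participant who triggers at visit 3 or 4 leaves before the day-21 biopsy and has no AIM2 or IFI16 change score. Under 6.2 as written, nothing stops the same participant from continuing. If the trigger is first seen at visit 5, no section says whether the biopsy is taken. Who contributes to the primary comparison then depends on which section was followed.

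**Exclusion based on the outcome.** Section 6.2 drops a site because its CAL worsened, and there is no matching rule for sites whose CAL improved. Only the loss tail is cut, so the analysed sites cannot show a recorded loss above 2 mm. The estimated CAL change moves toward no loss whenever the rule is applied.

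**Working it through.** **1. The rules side by side**

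| Section | Trigger | Site data | Participant |
|---|---|---|---|
| 2.3.1 | any site | not mentioned | exits |
| 6.2 | any site | excluded from analysis | not mentioned |
| 7.1 | test sites | not mentioned | exits |

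Sections 2.3.1 and 7.1 agree on the consequence and differ on the trigger. Section 6.2 differs from both on the consequence.

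**2. Size of the bias per event**

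Inputs:
- Recorded loss at a triggering site. The CAL definition in 7.1 says "If a CAL reading falls between two millimeter readings, the rule shall be to round down", so readings are whole millimetres and a loss above 2 mm is a recorded loss of at least 3 mm.
- Sites analysed, k. Section 11.3 does not say whether test-area or full-mouth CAL is modelled. Six sites per tooth is stated for the gingival and plaque indices and is assumed here for CAL. Section 5.1 requires "Subjects must have at least 2 natural adjacent teeth in two posterior sextants", giving 2 × 6 = 12 sites. A six-tooth test area (assumed) gives 36. The 20-tooth minimum in 5.1 gives 120.
- Other sites are assumed to change by 0 on average.

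Formulas: shift in a participant's mean = 3/k mm; shift in the group mean = (3/k) × n/36, with n participants each losing one site.

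| k | Participant's mean | Group mean, n = 1 | Group mean, n = 4 |
|---|---|---|---|
| 12 | 0.250 mm | 0.0069 mm | 0.0278 mm |
| 36 | 0.083 mm | 0.0023 mm | 0.0093 mm |
| 120 | 0.025 mm | 0.0007 mm | 0.0028 mm |

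A simulated site-level mixed model (36 participants, 12 sites, random participant intercept, 20 runs) gave the same difference between keeping all sites and excluding: 0.007 mm for n = 1 and 0.028 mm for n = 4.

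**3. Direction under a range of assumptions**

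The documents give no mean or SD for site-level CAL change, so these are assumed. Changes were drawn from a normal distribution, rounded to whole millimetres, and compared with and without values above 2 mm.

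| Mean, SD (mm) | Sites dropped | Mean, all sites | Mean, kept sites |
|---|---|---|---|
| 0, 0.6 | 0.002% | 0.000 | 0.000 |
| 0.2, 0.8 | 0.2% | 0.200 | 0.195 |
| 0.2, 1.0 | 1.1% | 0.200 | 0.169 |
| 0.5, 1.0 | 2.3% | 0.500 | 0.440 |
| 1.0, 1.5 | 15.8% | 1.000 | 0.554 |

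The shift was never upward. The last row is the extreme of the grid and is not a forecast.

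**4. Any site against test sites**

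If p is the chance of a trigger per site-visit, independent across sites and the three follow-up visits, then P(participant triggers) = 1 − (1 − p)^(3k). The values of p are assumed.

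| p | 120 sites (any site) | 12 sites (test sites) |
|---|---|---|
| 0.01% | 3.5% (1.3 of 36) | 0.4% (0.1 of 36) |
| 0.1% | 30% (10.9 of 36) | 3.5% (1.3 of 36) |

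The wording of the trigger changes the number of exits by close to a factor of ten.

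**5. Retention allowance**

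Section 11.3 expects about 64 of 72 day-21 samples: (72 − 64)/2 = 4 losses per group from all causes. Each exit before visit 5 under 2.3.1 or 7.1 uses one of the four. Under 6.2 as written it uses none.

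**6. What the earlier studies can say**

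Their sizes and exit rules are not in the documents. As illustration, zero withdrawals among an assumed 50, 100 or 200 people gives a one-sided 95% upper limit of 1 − 0.05^(1/m) = 5.8%, 3.0% or 1.5%, which is 2.1, 1.1 or 0.5 of 36.

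**The case against.** The best opposing case has four parts.

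- **The sections may be cumulative.** Section 6.2 is silent on exit; it does not say the participant stays. One could read the three together: site treated, its data set aside, participant removed. The any-site wording in 2.3.1 follows a sentence on monitoring the experimental area and could mean the test sites. This reading is possible, but excluding one site has little purpose if the whole participant leaves, and the text still leaves any site against test sites open.
- **The effect is tiny and on a lesser endpoint.** Section 11.3 ties the clinical measurements to secondary hypotheses, 11.1 lists no CAL hypothesis, and the per-event group shifts are thousandths to hundredths of a millimetre. All of this stands. It limits the size of the bias, not its existence or direction.
- **Losing a few participants does not hurt power.** With the SD of 0.25 and correlation of 0.40 in 11.2, the SD of change is 0.25 × √(2 × 0.6) = 0.274. A two-sided t-test for a difference of 0.40 has power above 0.999 at 32 per group and 0.999 at 24; 9 per group still exceeds 80%. This also stands for that stated target. The problem is an undefined analysis population, not power.
- **Visit 5 has a clear default order.** Section 6.5 lists examination, biopsy, then root planing. That is a sensible default, but no section says it holds once the removal rule has been triggered.

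Setting aside a site's data after rescue is defensible. Deleting what was recorded before rescue is not.

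**Conclusion.** The concern holds and should be fixed. The conflict is on the face of the text: two sections remove the participant, one acts on the site, and the trigger is any site in two sections and test sites in the third. The exclusion in 6.2 depends on the outcome and is one-sided, so if followed it biases CAL change toward no loss.

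The likely size is small: 0.0007 to 0.028 mm in a group mean for one to four affected participants. That range assumes one 3 mm site each, six CAL sites per tooth, and no average change elsewhere. How often sites will progress is unknown; the plan expects it to be rare. The bias concerns CAL and does not act directly on the AIM2 and IFI16 comparison. That comparison is touched only through who remains to give a day-21 sample.

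**What to change.** 1. State one rule, in the same words, in 2.3.1, 6.2 and 7.1: which sites count, whether the site or the participant leaves, and whether a trigger found at visit 5 cancels the biopsy. The choice is the sponsor's.
2. Strike from 6.2 the clause that removes the site from data analysis.
3. Add to 11.3 that the mixed models keep all measurements up to and including the progression visit, taken before rescue, with exclusion of progressing sites only as a sensitivity analysis.
4. Report the number and percentage progressing in each group.

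The cost is wording in three sections and a short addition to 11.3. No new data or visits are needed, and rescue treatment is unchanged.

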6 STUDY SCHEDULE

6.1 Visit 1: Screening/enrollment

(Day -28 +/- 2 days)

- Informed Consent: Before recruitment and enrollment, each prospective candidate will be given a full explanation of the study, and allowed to read the informed consent form that has been approved by the Institutional Review Board. Qualified study personnel will directly ask the subject if he/she understands the implications of participating in the study. Subject will have the opportunity to ask questions and have answers related to the study participation. No protocol procedures will be performed prior to confirmation that the subject understands the procedures and risks. Once the subject confirms this understanding verbally, the subject will be asked to give consent to participate in the study by signing the informed consent form. The study personnel will provide copies of the signed informed consent forms to the subject.
- Study personnel will obtain medical history and demographics related to the participant, height and weight
- Study personnel will record the subject's vital signs (blood pressure and pulse).
- Female participants capable of child bearing will be given a urine-based pregnancy test.
- A dental examiner (calibrated dentist or dental hygienist) will perform an intraoral examination to verify no presence of oral pathology.
- Dental examiner will perform a comprehensive periodontal screening examination that includes Plaque Index (PI), Gingival Index (GI), Pocket Depth (PD), Bleeding on Probing (BOP) and Clinical Attachment Levels (CAL).
- Subjects in the categories of healthy (PPC-A, PPC-B) or severe disease (PPC-E, PPC-G) will be considered eligible for the study.
- If the participant meets eligibility criteria during the clinic visit, the participant will be invited to participate in the research study at that time. If determined non-eligible, the individual will be informed at that visit, or by telephone, to avoid an unnecessary visit. All subjects that complete visit 1 will receive a free parking voucher.
- If eligible, an alginate impression will be taken for stent fabrication

- The interproximal region of a tooth will be selected by a dental examiner for the first gingival biopsy (occurs at visit 2).
- The subject will receive a parking voucher for the Dogwood deck and be scheduled for visit 2

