- Study personnel will update medical history, including concomitant medication, enquire about potential adverse events related to the dental procedures and ask continuance criteria questions.
- Study personnel will record the subject's vital signs (blood pressure and pulse).
- A dental examiner will verify the previously performed intraoral exam and assess for potential adverse events.
- Dental examiner will perform a comprehensive periodontal screening examination that includes Plaque Index (PI), Gingival Index (GI), Pocket Depth (PD), Bleeding on Probing (BOP) and Clinical Attachment Levels (CAL).
- The dental examiner will collect two separate subgingival plaque samples from the interdental sulcus of the teeth that are selected for a gingival biopsy (see appendix II). Dental implant sites will not be considered for subgingival plaque samples.
- A small tissue biopsy sample will be removed from underneath the papillae, buccally and lingually, to include the col area of depth of the osseous crest of a tooth included in the SIBO model. The site for biopsy will be selected based on the tooth (included in the SIBO model) with the highest GI score. The biopsy will be collected by a study dentist and performed under local anesthesia. Absorbable sutures will be used to close the interproximal papillae.

- SRP may be initiated in individuals with severe periodontitis and will include the quadrant that received the gingival biopsy to allow optimal healing
- Adverse events will be monitored and recorded as necessary
- The subject will receive compensation for study participation, a parking voucher to the Dogwood deck. and visit 6 will be scheduled.

6.6 Visit 6: Final Visit (Post-biopsy follow-up; Prophylaxis; SRP may be completed up to visit 8 based on individual needs)

(Day 28 +/- 5 days)

Participants will be seen for a final visit at day 28 (+/-5 days). The following procedures will be performed at this visit:

- Study personnel will update medical history, including concomitant medication, enquire about potential adverse events related to the dental procedures and ask continuance criteria questions.
- Study personnel will record the subject's vital signs (blood pressure and pulse).
- A dental examiner will verify the previously performed intraoral exam and assess for potential adverse events.

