Gingival Tissue/Biopsy: Biopsy samples of gingival tissues will be collected from all individuals at baseline and 21-days of biofilm-overgrowth. A trained dentist will use a scalpel blade to collect 2 biopsy samples per subject for a total of 128 samples. Samples will be obtained using topical and local anesthesia. Each biopsy shall be ≤ 0.5 cm thick. Biopsies will only be collected from the papillae of posterior teeth. The scalpel blade shall be oriented in an inverse bevel direction to capture the base of the periodontal pocket or gingival sulcus. Each biopsy will contain oral epithelium, gingival connective tissues and loosely adherent cells lining the periodontal pocket. Papillae height will be retained by using vertical mattress suture technique, minimizing facial reduction, and coronal reposition of the flap. The biopsy wound will be undermined with minimal flap reflection and closed with a suture. Post-operative instructions, including placing ice over the surgical area and avoiding hot liquids for the remainder of the day, will be given to the subject.

Gingival biopsy samples will be bi-sectioned for immunohistochemistry/immunofluorescence imaging and mRNA expression.

1. For **RNA** extraction, samples will be immediately placed in RNeasy[®] (Ambion Inc.) which is an aqueous, non-toxic tissue storage reagent that rapidly permeates tissue to stabilize and protect cellular RNA *in situ* in unfrozen specimens. Samples will be placed in a microfuge tube containing ~1ml of RNeasy and kept at 4°C overnight, then RNeasy is removed. Samples will be stored at -80°C until used for analysis.
2. For **Immunohistochemistry/Immunofluorescence**, samples will be fixed in 4% paraformaldehyde and stored at -20°C for 24 hours and then placed in 70% ethanol for further analysis.

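### The day-21 biopsy site is picked by highest GI and the baseline site by no inflammation rule, so the change tested in 1a/1b can be shifted without a SIBO effect; the documents do not fix the size

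*Combined protocol and SAP*

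**What the plan says.** **Day-21 site (6.5).** "The site for biopsy will be selected based on the tooth (included in the SIBO model) with the highest GI score". The sentence does not name the visit whose GI counts; visit 5 is the natural reading.

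**Baseline site (6.1, 6.2, 7.3.1).** At visit 1, "The interproximal region of a tooth will be selected by a dental examiner for the first gingival biopsy". No GI or other inflammation criterion is attached. The only anatomical limit is "Biopsies will only be collected from the papillae of posterior teeth". The stent "will be used in a different sextant from the one that the biopsy was performed", so the two biopsies never come from the same sextant.

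**Appendix II.** It leaves the site at both visits to the dental provider, says sites are not standardized because dentition varies, and does not repeat the highest-GI rule. The supplemental materials are labelled as outside the protocol, although 6.2 and 6.5 refer to this appendix.

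**GI (7.1).** "Full mouth gingival scores shall be visually assessed by segmenting marginal and papillary units, 6 sites per tooth", on a four-point scale that runs from 0 to "3= Severe inflammation; marked redness and edema". How six scores become one tooth score is not stated.

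**Hypotheses and tests (11.1, 11.3).** 1a and 1b claim a temporal change in AIM2 and IFI16 induced by SIBO. A joint and then univariate signed-rank test is applied to visit 2 versus visit 5. Site does not enter the analysis, and no non-stent biopsy is taken at day 21.

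**The concern.** A paired change can be read as an effect of time or exposure only if both ends are sampled in the same way. Here one end is the most inflamed of several candidate teeth, and the other is whatever site the examiner chose. Section 11.1 cites models in which AIM2 and IFI16 are highly expressed under inflammation. If that also holds between sites within one mouth, picking the highest GI picks higher expression on average, whether or not the stent did anything.

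The test of zero change is what is exposed. A significant 1a or 1b result could come partly from site choice, and the planned analysis could not separate the two. Using different sextants, and sampling an inflamed SIBO site, are both reasonable choices; the gap is that the rule is not matched.

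**Working it through.** **1. The plan's own figure.** Section 11.2 gives one calculation on change: at least 80% power for a between-group difference of 0.40, with SD 0.25 and intra-subject correlation 0.40.
- SD of change = 0.25 × √(2 × (1 − 0.40)) = 0.274.
- With 32 per group, 80% power is reached at (1.960 + 0.842) × 0.274 × √(2/32) = 0.19, so the statement is true with room to spare. It concerns 1c. Nothing is given for 1a/1b.

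**2. Inputs.**
- From the plan: SD 0.25; correlation 0.40; GI scored 0–3; two-sided 0.05; 128 biopsies / 2 = 64 subjects, or 32 per group.
- Assumed, because the documents are silent: k, the number of candidate units; r, the between-site correlation of GI with expression; s, the share of within-person variance lying between sites; and three GI distributions (percent scoring 0/1/2/3: 15/45/35/5, 50/40/10/0, 80/17/3/0), with ties broken at random.
- All results are on the immunohistochemistry scale. Section 11.2 has no mRNA data to work from.

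**3. Expected shift with no SIBO effect.**
- Within-person SD = 0.25 × √0.60 = 0.194. With s = 0.5, between-site SD = 0.194 × √0.5 = 0.137.
- On a continuous GI scale, shift = E[max of k standard normals] × r × 0.137. For k = 3 this is 0.846 × 0.5 × 0.137 = 0.058 at r = 0.5, and 0.035 at r = 0.3.
- On the four-point scale, ties reduce it to 0.02–0.05 over r = 0.3–0.5.

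**4. What the shift does to the test.** With n = 64, the SE of the mean change is 0.274/8 = 0.034. A shift of 0.02 is 0.58 SE, and a normal approximation gives 9% rejection. A shift of 0.05 is 1.46 SE and gives 31%. Null simulations of the signed-rank test agree (k = 3, s = 0.5, one papillary unit chosen by GI, range over the three distributions):

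| r | n = 64 | n = 32 |
|---|---|---|
| 0 | about 5% | about 5% |
| 0.1–0.2 | 5–9% | 5–6% |
| 0.3 | 9–14% | 7–10% |
| 0.5 | 16–31% | 10–17% |

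**5. Selecting a tooth, as 6.5 says** (four teeth, s = 0.5, r = 0.5, n = 64). The unwritten details decide the result:

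| Tooth score | More inflamed papilla taken | Either papilla at random |
|---|---|---|
| Mean of six | 14–21% | 8–12% |
| Maximum of six | 9–12% | about 5–6% |

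**6. If the examiner already picks the highest-GI baseline site at visit 1** (k = 3, s = 0.5, r = 0.5, n = 64). Rejection is 7–11% if site deviations correlate 0.5 between visits 1 and 2, and about 5% if they persist fully.

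**7. Between-group tests 1c/1d** (32 v 32, k = 3). Under the common SD of 0.25, the shift is the same in both groups and cancels: about 5–6%. With the cross-sectional SDs of 0.14 and 0.27 that 11.2 also quotes, s = 0.5 and r = 0.3–0.5, rejection is 7–10%, against 5.5–6% at r = 0.

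**8. The same rule at both visits** (r = 0.5 unless stated, n = 64).
- Equal k, GI distribution and r: 4–6%.
- Two units in one sextant and four in the other: a shift of about 0.03 and 12–14% (s = 0.5), or 0.04 and 20–23% (s = 1), in either direction.
- GI moving from the mildest distribution at baseline to the most inflamed at day 21: a shift of 0.015–0.022 and 7–9%.
- r = 0.5 at baseline but 0.1–0.2 at day 21: a downward shift of 0.03–0.04 and 13–20%.

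**The case against.** - **The larger figures model a papilla, while 6.5 names a tooth.** This stands. With a six-score maximum and a random papilla there is almost no inflation. It is a reason to write the rule down.
- **The null is strained.** If expression follows inflammation, SIBO should raise it and 1a/1b are not null. If it does not follow SIBO-induced inflammation, GI at day 21 should be a weaker guide to expression than at baseline. This stands in part: pre-existing site differences can keep some correlation, but r = 0.1–0.2 gives only 5–9%.
- **Direction is not established.** This also stands. An examiner who favours inflamed sites at baseline shrinks the shift, and a strong enough preference could reverse it.
- **Matching can do harm.** If the GI–expression link is much weaker at day 21, matching creates a downward shift larger than the upward one it replaces (step 8). A reader might infer that a matched rule removes the bias; it does so only when candidate units, GI distribution and link are alike at both ends.
- **The primary objective is the between-group comparison, and non-standardization is declared.** The first part limits severity, but 11.1 lists 1a and 1b as primary too. Declaring that sites vary with dentition does not explain why only one of them is chosen on inflammation.

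**Conclusion.** The asymmetry is in the text and affects two hypotheses labelled primary, so matching the rule is a worthwhile, cheap improvement. Following the plan exactly can shift the 1a/1b change, upward if GI and expression are positively related between sites and the baseline choice is not itself driven by inflammation. The size is not fixed by the documents. With 64 subjects, illustrative null rejection runs from about 5% (no or weak link, or some tooth-score and papilla rules) to about 30% (k = 3, r = 0.5, half the within-person variance between sites).

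Stronger readings that the documents do not support:
- That the false-positive rate is known, or exceeds one half. Simulated values of 29–53% need all within-person variance to lie between sites, with selection by unit at r = 0.5.
- That 1c/1d are compromised. They are little affected under the common SD; a shift of 0.02–0.05 is also small beside the 0.40 in 11.2.
- That Appendix II overrides 6.5. It is less specific and labelled as outside the protocol, so it only needs to be brought into line.

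**What to change.** 1. Keep the baseline and stent sextants fixed at visit 1, since the impression is taken then ("If eligible, an alginate impression will be taken for stent fabrication"). Within the baseline sextant, choose the biopsy unit at visit 2 by the same GI rule as 6.5, using the GI exam that 6.2 already lists before the biopsy.
2. State once, for both visits: which visit's GI is used, how six scores form a tooth score, which papilla of the tooth is taken, and how ties are settled. Align 6.1, 6.2, 6.5 and Appendix II. Record the number of candidate units in each sextant.
3. Add to 11.3 a sensitivity analysis of 1a/1b using visit-2 GI and PD at both biopsied sites. Both are already recorded. Do not adjust for visit-5 GI, which SIBO is meant to change.
4. State as a limitation that matching reduces but does not remove the bias. A residual shift in either direction remains if candidate-unit numbers, the GI distribution or the GI–expression link differ between sextants or visits. Attribution to SIBO in 1a/1b also stays limited without a day-21 non-stent biopsy.

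Cost: protocol wording, one recorded count and one extra analysis, with no additional visit, exam or biopsy. The downside is that baseline tissue will be more inflamed, so the measured change may be smaller.
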